8.2 Different time-points

The following additional analyses will be conducted to explore the impact of Ashwagandha at different time-points:

- Analysis of the study outcomes at 1-month follow-up
- Analysis of the study outcomes at 2-month follow-up
- Analysis of the study outcomes at 3-month follow-up

We will also conduct a mixed-effect analysis treating each month of medication as a separate observation (i.e. dataset with one row per month), using the baseline value at the start of that month and endline value at the end, with observations clustered within participants using a multilevel model with participant-level random intercepts. This will increase the power of the analysis assuming that the trial medication will have measurable effect after 30 days of treatment, which some previous trials support⁶.

In addition to these analyses, description of the outcome data by arm and time point (baseline, month 1, month 2, month 3) will be presented in graphical format.

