3.2 Sample size

The original sample size planned for the trial was 2500. The justification for this given in the study protocol is as follows: "Published data from an online survey of Long COVID patients indicate that patients' grade distribution on the Post-Covid Functional Scale (scale 4 (severe) to 0 (none)) improved from of 3.4, 49.4, 35.1, 7.1 and 5.0% at 3 months to 2.1, 43.9, 35.1, 10.5 and 8.4% at 6 months². If Ashwagandha can improve symptoms to a similar extent at 3 months, this translates to an overall odds ratio of 0.71 on the ordinal logistic regression analysis (with an odds ratio less than one indicating a shift to a lower grade of symptoms). In order to improve symptoms with a more modest odds ratio of 0.75, a sample size of 2500 gives in excess of 90% (or 80% power to detect an even more conservative odds ratio of 0.80). An odds ratio of 0.75 would result in the percentages in each grade (grades 4 to 0) being 2.6, 43.1, 38.8, 9.0 and 6.6% in the Ashwagandha arm at end-line. The primary analysis will include adjustment for the baseline value of the primary outcome scale which is expected to increase the power further."

This sample size was proposed initially alongside a more simplified trial protocol in which Long COVID patients registered their interest online, were randomised online, and then posted the medications directly from the trial coordinating centre. However this model (which would have allowed much more rapid recruitment) was not permitted by the regulator (MHRA) who required clinician oversight of each patient including regular liver function monitoring. The MHRA-directed approach was adopted, which involved modifying the protocol to recruit and monitor through NHS GPs. It was agreed with the MHRA that after safety and effectiveness data from at least ~100 patients' had been gathered, we would submit the safety information and apply to relax the monitoring procedures to speed up recruitment. This initial safety-focussed phase of the trial has been completed although we opted not to continue the trial because of barriers faced in identifying and recruiting Long COVID patients. The trial is therefore expected to be underpowered for the primary outcome, although they will still be presented in adherence with the pre-specified protocol, and emphasis will be placed on the safety-related trial outcomes.

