6.1 Primary outcome

The primary analysis of the primary outcome will be an intention-to-treat complete case analysis at 3-month follow-up, adjusted for baseline level of the same outcome. Post-Covid Functional Status Scale will be analysed using ordinal logistic regression. No other adjustments will be made for the primary analyses, although additional secondary analyses adjusting for age (above or below median) and gender will be conducted (see section 8.4 below).

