6.2 Secondary outcomes

Due to the large number of secondary outcomes, the PROMIS-29+2 summary score and EQ-VAS score will be considered as 'key secondary outcomes' and only these (along with the primary outcome) will be taken forward into the additional analyses (section 8). For all secondary outcomes, the main analysis will be intention-to-treat complete case analysis at 3-month follow-up, and for continuous and ordinal outcomes these will be adjusted for baseline level of the same outcome. The statistical models that we plan to use for each outcome are listed below. Distributional checks will first be conducted to ensure that key assumptions for each planned model type are met, and if for any given outcome there are violations that threaten the validity of the proposed model type, that outcome will be binarized by the median value and analysed with binary logistic regression.

Ordinary least squares (linear) regression:

- Quality of life by PROMIS 29+2 summary score
- Self-reported fatigue by PROMIS 29+2 fatigue dimension
- Self-reported sleep disturbance by PROMIS 29+2 sleep dimension
- Self-reported anxiety by PROMIS 29+2 anxiety dimension
- Self-reported depression by PROMIS 29+2 depression dimension
- Self-reported social participation by PROMIS 29+2 social function dimension
- Self-reported physical function by PROMIS 29+2 physical function dimension
- Self-reported cognitive function by PROMIS 29+2 cognitive function dimension
- Self-reported pain interference by PROMIS 29+2 pain dimension
- Self-reported pain intensity by PROMIS 29+2 0-10 pain rating scale
- Health utility by EQ 5D-5L utility score
- EQ VAS score
- Self-reported work productivity by 0-10 scale on the work questionnaire (people out of work scored to 0)

Ordinal logistic regression:

- Self-reported breathlessness by modified MRC Dyspnoea Scale
- Other self-reported symptoms number (count) of other symptoms experienced (grouped into 5 groups according to the distribution)

Binary logistic regression

- Whether any hours of work were missed in the past 7 days (yes/no) (people out of work set to no)
- Other self-reported symptoms binary presence/absence of each of the 22 other symptoms asked (only including in the table those with at least 10 individuals reporting that symptom at baseline). If any other self-reported symptom (from the free-text field) was reported by at least 10 people at baseline, this can also be added.

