Dummy table illustrating the presentation of the primary and secondary analysis results is given in appendix table 3.

7 Evaluation of safety outcomes

A table will be presented with counts of the following adverse safety outcomes, by trial arm (appendix table 4):

- SUSAR
- Serious adverse event (SAE)
- Pregnancy
- Adverse reactions involving abnormal liver test results (adverse event designated as probably or definitely related to trial medication)
- All other adverse reactions
- Adverse events (designated possible or unlikely related to trial medication) involving abnormal liver test results
- All other adverse events (designated possible or unlikely related to trial medication)

Further description and discussion of any SUSAR, SAE, pregnancy, adverse reactions and abnormal liver test results will be provided in the text (as the numbers of these are anticipated to be few). For each abnormal liver test result, the status of liver function at baseline will be mentioned, as abnormal liver function at baseline is expected to be linked to abnormal results during follow-up (although numbers are expected to be too small to formally test this). All adverse events will be broken down into specific categories (e.g. headache, nausea, etc) by trial arm in an appendix table. We will also present adverse events by trial arm stratified by gender in the same appendix table.

Changes over time in liver function test (LFT) results by arm will be described through data visualisation. Specifically, we will plot the mean and standard error values of AST, ALT and bilirubin at baseline, month 1 and month 3 by trial arm. T-test for the differences in each LFT will be calculated at each timepoint, crudely and with adjustment for baseline level. The corresponding numerical results will be given in an appendix table.

8 Additional analyses

The following additional analyses will only be applied to primary and key secondary to avoid multiplicity of analysis results. Apart from the specific aspects mentioned, each analysis will be the same as described in section 6.

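### The month-by-month mixed model in SAP section 8.2 adjusts months 2 and 3 for post-randomisation values, so its coefficient is not the 3-month effect and its stated power gain is not assured

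*SAP*

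**What the plan says.** Section 8.2 adds a mixed-effect analysis to the separate month-1, month-2 and month-3 analyses. Each month of medication is one observation, "using the baseline value at the start of that month and endline value at the end". A random intercept for each person accounts for the repeated rows. The reason given is: "This will increase the power of the analysis assuming that the trial medication will have measurable effect after 30 days of treatment". The SAP gives no power figure, within-person correlation or effect trajectory.

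The opening of section 8 settles how the baseline enters: "Apart from the specific aspects mentioned, each analysis will be the same as described in section 6". In section 6 baseline is an adjustment covariate, and the primary analysis is an "intention-to-treat complete case analysis at 3-month follow-up, adjusted for baseline level of the same outcome". Under section 6.2 the additional analyses cover the PCFS, the PROMIS-29+2 summary score and the EQ-VAS.

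**The concern.** Only the month-1 row is adjusted for a value taken before treatment. The month-2 row is adjusted for the month-1 outcome and the month-3 row for the month-2 outcome. If the drug has begun to work, those covariates already carry part of its benefit, and adjusting for them leaves only what the covariate does not explain. The result answers a different question from the objective in section 2, which is functional status at 3 months. Because the SAP presents it as a more powerful analysis without naming the change of estimand, a reader would set it beside the primary estimate and take it for a smaller effect of the same kind.

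A previous outcome is also correlated with the participant's own intercept, while the model treats the two as independent. The rationale for the model is power, so it matters whether the gain is real.

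**Working it through.** **The plan's own figures.** The mixed model has no stated figure, but section 3.2 does. Take the control grades "3.4, 49.4, 35.1, 7.1 and 5.0% at 3 months", 1:1 allocation and two-sided 0.05 (assumed; the SAP states no alpha). Then V = (N/12)(1 − Σp̄³) and power = Φ(|ln OR|√V − 1.96).
- OR 0.75, N = 2500: Σp̄³ = 0.150, V = 177.1, power = Φ(0.2877 × 13.31 − 1.96) = 96.9%, in line with the stated excess over 90%.
- OR 0.80: 84.2% with no dropout and 80.3% with 10% dropout, so the stated 80% is reached.
- OR 0.75, N = 105: V = 7.44, power about 12%.

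**Size of the coefficient.** Let δ be the 3-month effect and b the slope on the start-of-month value.
- Full effect by month 1: the three rows carry δ, (1−b)δ and (1−b)δ, so the average is (3−2b)/3 of δ. At b = 0.7 this is 0.53.
- Linear build-up: the rows carry δ/3, (2−b)δ/3 and (3−2b)δ/3, so the average is (2−b)/3 of δ. At b = 0.7 this is 0.43.

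Simulation over correlations of 0.5 to 0.85 and several trajectories gave ratios of 0.39 to 0.70 for continuous outcomes and 0.46 to 0.74 for the PCFS.

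**The random intercept.** Take compound symmetry with correlation ρ and unit variance, so b = ρ. The row residual is y(t) − ρy(t−1), with variance 1−ρ², covariance −ρ²(1−ρ) between adjacent months and ρ(1−ρ)² two months apart. At ρ = 0.7 these are 0.51, −0.147 and 0.063. A random intercept cannot produce a negative covariance, so its variance goes to zero and the rows are treated as independent. The variance of the sum of the three residuals is then taken as 3 × 0.51 = 1.53, when it is 1.53 + 2(−0.294 + 0.063) = 1.068. The standard error is too large by √(1.53/1.068) = 1.197, and type I error is 2Φ(−1.96 × 1.197) = 0.019. Simulation at 0.7 gave about 0.025 with the intercept variance zero in every run; across the compound-symmetry cases type I error was 0.013 to 0.035. Under AR(1) it was nearer nominal (0.057 at 0.7, 0.037 at 0.85).

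**Power, continuous outcome.** Assumptions: N = 105, no dropout, 3-month effect 0.4 SD. At compound symmetry 0.7, full effect by month 1:
- 3-month ANCOVA: SE = √(0.51 × 4/105) = 0.139; Φ(0.4/0.139 − 1.96) = 0.82.
- Planned model: coefficient 0.213, model SE √(1.53/9 × 4/105) = 0.0805, true SE √(1.068/9 × 4/105) = 0.0672; Φ((0.213 − 1.96 × 0.0805)/0.0672) = 0.80.
- Randomisation baseline in all rows, average over months: variance (3 × 0.51 + 6 × 0.21)/9 = 0.31, SE 0.109; Φ(0.4/0.109 − 1.96) = 0.96.

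The same formulas give the other compound-symmetry (CS) rows below; the AR(1) rows are simulated.

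| Correlation | Effect | 3-month ANCOVA | Planned model | Randomisation baseline, average |
|---|---|---|---|---|
| CS 0.5 | full by month 1 | 0.66 | 0.79 | 0.89 |
| CS 0.7 | full by month 1 | 0.82 | 0.80 | 0.96 |
| CS 0.8 | full by month 1 | 0.93 | 0.85 | 0.99 |
| AR(1) 0.7 | full by month 1 | 0.59 | 0.74 | 0.82 |
| AR(1) 0.85 | full by month 1 | 0.72 | 0.81 | 0.94 |
| CS 0.5 | linear | 0.66 | 0.54 | 0.56 |
| CS 0.7 | linear | 0.82 | 0.59 | 0.69 |
| CS 0.8 | linear | 0.93 | 0.70 | 0.82 |
| AR(1) 0.7 | linear | 0.57 | 0.55 | 0.48 |
| AR(1) 0.85 | linear | 0.74 | 0.73 | 0.66 |

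**Power, PCFS.** Scaled so that the 3-month analysis has 80%, the planned model has 88-94% with the full effect by month 1 (randomisation baseline 95-97%) and 67-84% with linear build-up (68-83%). These are rough. They come from one simulated data set of 20,000 per case and a pooled ordinal logit with clustered standard errors. At CS 0.7 the 3-month log odds ratio came out at −0.338, −0.459 and −0.389 under three trajectories that share the same month-3 effect. At about OR 0.75 and N = 105 every PCFS version has roughly 10-25% power.

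**The case against.** The power statement is conditional on a measurable effect after 30 days. If the effect is full by then, the planned model often does better than the single 3-month analysis: 0.74 against 0.59 under AR(1) 0.7, and 88-94% against 80% for the PCFS. A smaller coefficient comes with a smaller standard error. This stands, so a reader who infers that the power claim fails outright goes too far. But the condition as worded does not require the full effect by month 1. Under linear build-up a third of it is present at 30 days, and power is then usually lower.

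A reader might also infer that the coefficient is half the true effect. That value belongs to a lag slope near 0.7, which is an assumption. Nor is the coefficient meaningless: section 8.2 says each month is a separate observation, and a per-month effect given starting status can be interpreted once it is labelled.

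A reader might fear a false positive. With no treatment effect, randomisation leaves the lagged values balanced between arms, and under compound symmetry the test errs on the conservative side. The risk is understatement.

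Lastly, the documents do not present this model as the remedy for stopping at 105. The background and section 3.2 accept that the primary outcome is underpowered and move the emphasis to safety. The primary analysis is unaffected, and the direct monthly analyses and plots will stand beside this estimate.

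**Conclusion.** The point holds, at moderate weight. From the text alone, two of the three rows adjust for post-randomisation outcomes, and the resulting estimand differs from the 3-month effect without being labelled. In every case tried the coefficient was smaller, at about 0.4 to 0.75 of the 3-month effect.

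The random intercept and the lagged covariate do not fit together: under compound symmetry the intercept variance is usually zero and, at correlation 0.7, the test is conservative.

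The gain in power is not assured. For continuous outcomes with the full effect by month 1, the change runs from about −8 points (CS 0.8) to about +16 (AR(1) 0.7). Compared with using the randomisation baseline, part of the available gain is lost (CS 0.5: 0.79 against 0.89) or all of it (CS 0.7: 0.80 against 0.96, with 0.82 from the 3-month analysis alone). With linear build-up the change runs from about −23 points to near zero.

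The correlations, trajectories, 0.4 SD effect and absence of dropout are assumptions. The 0.4 SD is about 2.5 times the design effect (ln(1/0.75)/1.81 = 0.16 SD), so the power values serve to compare the analyses and do not forecast this trial.

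**What to change.** In every row, use the pre-randomisation value as the only outcome covariate, with arm, month, arm-by-month and a participant random intercept (ordinal mixed model for the PCFS, linear for the PROMIS-29+2 summary and EQ-VAS). Report the month-3 contrast as the estimate comparable with the primary analysis, noting that section 3.4.2 can place a month-2 survey in the primary analysis, and the months 1-3 average as secondary. Reword the power sentence to say that a gain is expected for the average if the effect is largely present by month 1 and persists. If the planned model is kept as well, label its coefficient as a per-month effect given the value at the start of the month.

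The cost is SAP wording and a small code change on the same data. Section 4.2 requires SAP approval before unblinding, so the change belongs before that. The model also keeps participants who have only month-1 or month-2 data, whom section 4.5 excludes from the primary analysis.

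The limits should be stated. The gain shown above belongs to the average; with complete data the month-3 contrast is about as precise as the single 3-month analysis. If the effect builds slowly, the average also understates the 3-month effect and may have no more power than that analysis (0.69 against 0.82 at CS 0.7), and under AR(1) it falls below the planned model. At the design odds ratio and N = 105, every PCFS version stays underpowered.

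### In the section 8.2 month-row mixed model, a random intercept alone may leave the confidence intervals for the PROMIS summary score and EQ-VAS too wide, by about 0 to 35% depending on a within-person correlation the SAP does not give

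*SAP*

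**What the plan says.** SAP section 8.2 adds a mixed model to the separate analyses at months 1, 2 and 3. Each month of medication contributes its own row, "using the baseline value at the start of that month and endline value at the end". The repeated rows of one person are handled by a single provision: "observations clustered within participants using a multilevel model with participant-level random intercepts". No other residual correlation structure and no robust standard error is named.

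The opening of section 8 says: "Apart from the specific aspects mentioned, each analysis will be the same as described in section 6". Section 6.2 says that "for continuous and ordinal outcomes these will be adjusted for baseline level of the same outcome". The start-of-month score therefore enters as a covariate, and the outcome is not a change score. Section 8 is limited to the PCFS and the two key secondary outcomes, the PROMIS-29+2 summary score and EQ-VAS. Section 6.2 assigns both of the latter to linear regression.

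The reason given for the model is: "This will increase the power of the analysis assuming that the trial medication will have measurable effect after 30 days of treatment".

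**The concern.** A survey score from the end of month 1 is used twice: as the outcome of the month-1 row and as the start value of the month-2 row. The same holds for the score from the end of month 2. A score that is high by chance gives a positive residual in the first of these rows. In the next row it raises the predicted value and so pushes the residual down. If that mechanism dominates, rows from one person vary in opposite directions. A random intercept can only describe rows that vary together.

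The fitted intercept variance then goes to its boundary of zero, and the software computes standard errors as if every row came from a different person. With negative correlation this overstates the uncertainty. Intervals would be too wide and type I error would be below 5%, so power would be lost in the one analysis the SAP justifies by a gain in power. A reported between-person variance of zero would also be hard to explain in a trial report.

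**Working it through.** The SAP states no standard error, correlation or power figure for this model, so there is no figure to reproduce. The check is algebra supported by simulation.

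**Inputs.** Up to three rows per participant, start value as covariate, random intercept only (sections 6.2, 8 and 8.2). Allocation 1:1 (section 3.3), 105 recruited (introductory text). Assumed: 100 or 104 participants with complete data, and the correlation pattern between monthly scores.

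**Algebra under equal correlation.** Let scores have unit variance and correlation ρ between any two months, and let the slope on the start value be ρ. The residual of row k is Y(k) − ρY(k−1).

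- Residual variance: 1 − ρ².
- Adjacent rows: covariance ρ − ρ − ρ² + ρ³ = −ρ²(1 − ρ), so correlation r1 = −ρ²/(1 + ρ).
- Rows 1 and 3: covariance ρ − 2ρ² + ρ³ = ρ(1 − ρ)², so correlation r2 = ρ(1 − ρ)/(1 + ρ).
- Standard error assuming independence, divided by the true value: √[3/(3 + 4·r1 + 2·r2)].

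Example, ρ = 0.7: r1 = −0.49/1.7 = −0.288 and r2 = 0.21/1.7 = 0.124. The denominator is 3 − 1.153 + 0.247 = 2.094, and √(3/2.094) = 1.20.

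The within-person term 4·r1 + 2·r2 equals 2ρ(1 − 3ρ)/(1 + ρ). It is negative once ρ exceeds 1/3, which is why the intercept variance is driven to zero at higher correlations.

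**Simulation.** Null data, REML random-intercept fit with arm, month and start value, several independent sets of 1,500 to 3,000 runs. Ranges span the sets.

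| ρ | r1 | Ratio, algebra | Ratio, simulated | Intercept variance zero | Type I error |
|---|---|---|---|---|---|
| 0.4 | −0.11 | 1.02 | 0.98–1.03 | – | about 4% |
| 0.5 | −0.17 | 1.06 | 1.01–1.06 | about 90% | 3.3–4.1% |
| 0.6 | −0.23 | 1.12 | 1.06–1.12 | 99% | 3.0–3.4% |
| 0.7 | −0.29 | 1.20 | 1.16–1.20 | 100% | 2.0–2.3% |
| 0.8 | −0.36 | 1.31 | 1.26–1.36 | 100% | 0.9–1.5% |

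**Other patterns.**

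- First-order Markov (AR(1)): the adjacent covariance is ρ − ρ − ρ³ + ρ³ = 0. Simulated ratio 0.99–1.03.
- Stable level + autoregressive part + noise: 1.07–1.13, with 1.09 typical.
- Random walk + noise: 1.07–1.10.
- Random slopes: 0.99–1.06.
- PCFS, cut into five grades at the SAP's planning percentages: 0.99–1.10.

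**Participant-clustered robust standard errors on the same rows (continuous outcomes).** Ratio 0.97–1.04 and type I error 3.8–5.6% in every pattern tried.

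**What the coefficient estimates.** Let the true effect at month 3 be d.

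- Effect constant from month 1: the rows carry d, d(1 − ρ) and d(1 − ρ), with mean d(1 − 2ρ/3). For d = 0.5 SD and ρ = 0.6 or 0.7 this is 0.30 or 0.27 SD.
- Effect rising linearly to d: the mean is d(2 − ρ)/3, that is 0.23 or 0.22 SD.

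Simulation gave 0.27–0.31 and 0.22–0.24, against 0.50 from month-3 ANCOVA on the randomisation baseline.

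**Power at ρ = 0.6 / 0.7 / 0.8, effect 0.3 SD at month 3.**

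| Effect pattern | Month rows, model SE | Month rows, robust SE | Month-3 ANCOVA |
|---|---|---|---|
| Rising linearly | 32 / 34 / 41% | 40 / 48 / 63% | 47 / 55 / 71% |
| Constant from month 1 | – | 57 / 65 / 76% | 46 / 56 / 71% |

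**The case against.** A reader might infer that chaining the rows by itself makes them negatively correlated, so that the intervals are certainly too wide. The SAP does not support that. It adjusts for the start value, and with that covariate the sign and size depend on how scores evolve. Under a first-order Markov pattern, or equal correlation of 0.4 or less, there is essentially no excess. The larger figures need correlations of 0.7 to 0.8 that do not decay, and the SAP gives no correlation. This objection stands, and it is why the point is stated conditionally.

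It also stands that the stakes are modest. The main analyses in section 6 use one outcome per person and are untouched. The SAP already expects the primary analysis to be underpowered and puts the emphasis on safety. The error is conservative, so it cannot create a false claim of benefit.

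A further objection is that the same sentence of 8.2 holds a larger problem: the start values of months 2 and 3 are post-randomisation and absorb earlier treatment effect. That is correct, and robust standard errors do not address it. Nor should a reader infer that they restore a power advantage. With a linearly rising effect the model stays weaker than the planned month-3 analysis.

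What remains is that a pure Markov pattern assumes neither a stable person level nor measurement noise. That is hard to believe for self-reported scores in a persistent condition, and the mixed patterns still show an excess of about 7 to 13%.

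**Conclusion.** The point holds conditionally and is at the optional level. In the 8.2 month-row model the random intercept cannot represent negative correlation between adjacent rows. If scores are a stable level plus monthly noise, its variance usually falls to zero. Model-based intervals for the PROMIS summary score and EQ-VAS may then be too wide by about 0 to 35%. The top of that range is the highest simulated value at an assumed equal correlation of 0.8, where the algebra gives 31%. PCFS is little affected.

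These sizes rest on assumed correlations, about 100 participants and complete data. Only the interval is at issue here. The coefficient is a month-step quantity, not the 3-month effect, and the gain in power that 8.2 asserts depends on the time course of the effect. The SAP's own condition, a measurable effect after 30 days, is not enough: in the rising-effect scenario a third of the final effect is present by then, and the model still has less power than month-3 ANCOVA.

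**What to change.** In section 8.2, state that confidence intervals and p-values of the month-row model come from participant-clustered robust (sandwich) standard errors, with a t reference for about 100 clusters, and that the random intercept is not relied on to account for the repeated rows. In the same place, make "This will increase the power of the analysis" conditional: power may rise if an early effect is sustained, but a gain over the month-3 analysis is not assured. Add that the coefficient is not the 3-month effect, because the start values of months 2 and 3 are measured after randomisation.

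The cost is a few sentences in the SAP and one line of code. The downside is a slightly more variable standard error, which is small with about 100 clusters. Where the correlation pattern causes no problem, the robust intervals remain valid and little is lost.
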